inflammation in metabolically-impaired individuals^{12,14,23,24}. Elevations in a range of inflammation biomarkers has been associated with severity of depression^{25,26}.

Although KDs have been proposed as a treatment option for mental health disorders, including schizophrenia²³ and depression⁷, few human clinical trials have tested the efficacy of this eating pattern specifically in a population of adults with major depression. In patients with type 2 diabetes (n=262) prescribed a KD using a novel virtual care model (Virta Health), we observed significant improvements in depressive symptoms after 10-weeks, which were directly correlated with the degree of carbohydrate restriction and nutritional ketosis as assessed by blood concentrations of ketones^{27,28}.

IMPACT

The overarching goal is to perform a pilot study to: (1) demonstrate that a well-formulated KD can be implemented in a university counseling treatment program for major depression, and (2) test whether such a program results in reductions of symptoms of depression. We plan to recruit 60 students with major depression who will receive coaching and support on a KD over a 12-week period; this will demonstrate initial feasibility of the diet. We hypothesize that participants will demonstrate improvements in metabolic health, mental health, cognition, and brain function (using Magnetic Resonance Imaging; MRI)²⁹. The data from this pilot study will be used to generate effect size estimates to inform the design of an intervention study to compare efficacy of a KD to standard diet and/or other diet treatment strategies. The results from this open-trial will also be valuable for providing safety information and providing relevant mechanistic information regarding KD-induced improvements in depression.

RESEARCH STRATEGY

This will be a single arm prospective trial assessing feasibility of implementing a KD in up to 60 participants with depression over 12-weeks. Participants who are MRI eligible will also have the option to complete pre- and post-intervention brain MRI. After enrollment, participants will complete a battery of baseline tests. The intervention will last 12-weeks with the primary efficacy outcomes assessed bi-weekly and other secondary/exploratory outcomes assessed at time points detailed in **Table 1**. Participants will receive standard of care clinical treatment for depression through the OSU Counseling and Consultation Services (CCS) throughout the intervention.

OUTCOMES

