Primary Outcomes. Adherence will be determined by the number of participants completing the 12-week intervention. We expect >80% of enrolled participants to complete the 12-week trial. Additionally, we will determine the number of participants who consistently maintain a level of nutritional ketosis (average ketones ≥ 0.5 mM).

The primary efficacy outcome will be depression score as assessed by PHQ-9 and HRSD. The self-reported PHQ-9 is a measure of depression symptom severity. It maps onto DSM-5 criteria for Major Depressive Disorder and is widely used in both clinical and nutrition research settings. The HRSD is an observer-rated measure of depression mostly used in research settings; the HRSD will be used to provide objective and standardized ratings of symptom severity, including ratings

that require external observation such as psychomotor retardation. The PHQ-9 and HRSD will be administered bi-weekly to provide a trajectory of depression symptoms.

Secondary Outcomes. In addition to changes in symptoms of depression, we will assess changes in a number of metabolic markers and cognitive markers of psychological health. We will assess the following to quantify these changes: Body weight, body composition, blood pressure, glucose, insulin, HbA1c, chemistry panel, lipids, and cognitive measures, structural and functional brain MRI). To examine changes in inflammation, we will assess the following markers: interleukin 1, interleukin 6, C-reactive protein, tumor necrosis factor-alpha, and WBC count with differential.

PARTICIPANTS

We expect to enroll up to 60 young adults with major depression into a KD intervention over a 12-week period. Participants will be able to pick up study fliers or will be handed fliers by CCS team members. Study fliers will include all inclusion and exclusion criteria and will provide potential participants with research team contact information. Participants must meet all inclusion criteria and none of the exclusion criteria as indicated on a prescreening checklist before baseline testing. Pre-screening and BL inclusion/exclusion criteria is outlined below.

Inclusion Criteria:

- OSU students (age 18-30 years at the time of enrollment) with confirmed major depressive disorder as determined by SCID-5 diagnosis at baseline testing.
- Currently engaged in counseling treatment for depression at CCS
- Available for a 12-week period and indicate willingness and ability to eat KD foods as prescribed

Exclusion Criteria:

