The diet intervention will start after all baseline testing is complete. Participants will receive extensive education and ongoing support from the dietetic team to achieve the nutritional goals of a well-formulated KD. Each participant may require slightly different levels of coaching depending on their baseline knowledge and individual situation. Thus, the intensity of engagement may vary across participants. We plan to provide a portion of their caloric intake in the form of staple food items in order to offset participant food costs, ensure nutrient quality, and facilitate adherence.

The KD will follow general principles as we have described³⁰ with the aim to achieve blood ketones >0.5 mM, which will require most participants to consume <50 g/day carbohydrate and ~1.5 g/kg reference weight protein. Fat will comprise the remaining calories with an emphasis on monounsaturated and saturated sources from whole foods. A wide range of foods will be incorporated including non-starchy vegetables, fruits (berries, olives, tomatoes, lemons/limes), meats (beef, chicken, pork, fish, lamb), nuts and seeds, oils (olive, canola, coconut), cheese, butter,

cream, eggs, and fatty fish (salmon, sardines). Nutritional ketosis is associated with natriuresis that will lead to sodium and fluid loss if the extra sodium excreted is not compensated by individualized intakes. If untreated, the resultant hypovolemia can manifest in side effects and adrenal stress (often mis-characterized as ‘keto-flu’) that disrupts body fluid, electrolyte, and mineral status. Thus, slightly higher sodium and potassium intakes are required to offset the natriuresis, which will be achieved through the provision of broth/LMNT electrolyte packs and appropriate food sources and cooking methods. In addition, neuro-muscular irritability characterized by muscle cramping will be addressed with individualized supplementation with oral magnesium and calcium. Shelf stable items such as high-quality fats/salad dressings, salmon & sardine packets, jerky, cheese whisps, nuts and seeds, will be included in the starter and replenishing kits.

DATA ANALYSIS AND STATISTICAL METHODS

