The Investigator is responsible for ensuring that participants' anonymity will be maintained. For all the data collected over the course of the study for each participant (i.e., records, biological samples and questionnaires) a unique subject identifier (i.e., a code) will be assigned and used instead of the subject's name. The code for each participant which links the subject name with their identifier will only be available to research personnel. Electronic CRFs or other documents will identify participants by initials, number, or code, and not by name. The Investigator will keep a separate log showing codes, names, and addresses. Any records that contain the subject's name and identifier will either be stored in the Clinical Psychology file storage room in a file cabinet (locked) or protected on a computer via password protection on the individual digital file and password protection on the computer the file(s) are stored on. All other records that contain the

subject identifier only will also be kept in either a file cabinet in our locked file storage room or on a password protected computer. Biological samples collected from each participant will be kept in a storage freezer labelled only with the subject identifier. Subject names will never be used in any presentation or publication resulting from this study. The records will be maintained until the data are published and up to a maximum of ten years after the completion of the study. All records or biological data obtained after signing of the informed consent (including the screening visit, even for subjects that are not eligible for participation in the study) are treated with the same confidentiality safety measures as those subjects who qualify. Any information obtained during the prescreening for participants that were not eligible will be deleted. [Any potential incidental findings from MRI, blood biomarkers, etc. will be shared with the participant. Incidental findings from the MRI imaging will be reported to the participants primary care physician within 30 days of finding. The remaining information \(ie. Blood biomarkers\) is non-diagnostic and will be provided so the participant may choose to share with their physician.](#)

5. Withdrawal of Participants from the Study

Participants may be removed from the study for any of the following reasons:

- A participant requests discontinuation;
- The Investigator initiates removal for medical or compliance reasons;

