- Occurrence of any AE or condition that could, in the Investigator's opinion, interfere with the evaluation of the effect of the study beverage or put the participant at undue risk.

It is understood by all concerned that an excessive rate of withdrawals can render the study uninterpretable, therefore, unnecessary withdrawal of participants should be avoided. Should a participant decide to withdraw, all efforts will be made to complete and report observations as thoroughly as possible. In the event that a participant is withdrawn from the study, the reason for the withdrawal will be documented.

Reference List

1. Organization WH. Depression. [Online]. 2021; <https://www.who.int/news-room/fact-sheets/detail/depression>. . Accessed October 22, 2021.
3. Rosner RI. Making a Case for Interpersonal Psychotherapy. *PsycCRITIQUES*. 2012;57(41).
6. Phillips MC. Metabolic Strategies in Healthcare: A New Era. *Aging and Disease*. 2021:0-

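### The adverse-event removal reason refers to a study beverage this diet trial does not have, and the promise to keep collecting observations does not cover participants whom the investigator removes

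*Protocol*

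**What the plan says.** The list in Protocol, Conduct of the Study, item 5 (Withdrawal of Participants from the Study) opens: "Participants may be removed from the study for any of the following reasons". After the participant's own request come two investigator grounds. One reads: "The Investigator initiates removal for medical or compliance reasons". The other is an adverse event or condition judged by the investigator as liable to "interfere with the evaluation of the effect of the study beverage or put the participant at undue risk".

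The same item says that unnecessary withdrawal should be avoided and that the reason is documented whenever a participant is withdrawn. On further data it says: "Should a participant decide to withdraw, all efforts will be made to complete and report observations as thoroughly as possible".

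The intervention is described under Research Strategy: "This will be a single arm prospective trial assessing feasibility of implementing a KD in up to 60 participants with depression over 12-weeks". The nearest thing to a drink is in Dietary Intervention, where added sodium and potassium is something "which will be achieved through the provision of broth/LMNT electrolyte packs and appropriate food sources and cooking methods". That is support for the diet, not the item under evaluation.

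On aims, the Impact section states: "The results from this open-trial will also be valuable for providing safety information". On the first primary outcome, the Outcomes section states: "Adherence will be determined by the number of participants completing the 12-week intervention". Data Analysis and Statistical Methods plans a linear mixed model for the depression scores, with missing data handled under a missing-at-random assumption.

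**The concern.** There are three faults, the first of them clerical.

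- **Wrong object.** The bullet names an intervention that appears nowhere else in the Protocol, so as written it cannot be applied.
- **Wrong kind of ground.** With the diet substituted, possible interference with the effect evaluation becomes a reason to end study participation. It is joined to undue risk by an 'or', so it applies with no safety concern present. Adverse events on the diet are among the things this single-arm pilot is meant to report, so they should not be a reason to stop observing someone.
- **Gap in follow-up.** The sentence on completing observations covers the participant who decides to leave. For a participant whom the investigator removes, only the reason is promised.

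At stake are the later depression scores and side-effect reports of people who had an adverse event or a new condition. A statistical analysis plan can choose how to analyse missing scores, but it cannot recover scores that were never collected. The point therefore belongs in the protocol.

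**Working it through.** The Protocol gives no figure on this point, so there is nothing to reproduce. The check is mainly a comparison of passages.

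**1. Object of the rule.** Research Strategy and Dietary Intervention describe a 12-week ketogenic diet. Only the withdrawal bullet mentions a beverage under study. The two must be reconciled.

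**2. What removal ends.** The opening line of item 5 speaks of removal from the study. Nothing in the item separates stopping the diet from ending assessments.

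**3. Who is covered by continued observation.** The complete-observations sentence is conditional on the participant's own decision. The next sentence, on documenting the reason, covers anyone withdrawn. Investigator-removed participants get the second commitment but not the first.

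**4. What can be lost.** In Table 1, PHQ-9 (like WHO-5) is due after baseline at weeks 2, 4, 6, 8, 10 and 12. HRSD and the side-effect survey are due after baseline at weeks 6 and 12 only. If assessments stop at removal, the scheduled post-baseline assessments lost are:

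| Removal | PHQ-9 (of 6) | HRSD (of 2) | Side-effect survey (of 2) |
|---|---|---|---|
| before week 2 | 6 | 2 | 2 |
| after week 4, before week 6 | 4 | 2 | 2 |
| after week 6, before week 8 | 3 | 1 | 1 |

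Anyone removed before week 6 has no scheduled on-diet side-effect survey and no post-baseline HRSD. If baseline enters the model as a covariate, which the analysis section leaves open, that person contributes nothing to the HRSD model. (The Outcomes section gives HRSD as bi-weekly. Table 1, its footnote and the Testing Visits text give baseline, week 6 and week 12, and those are used here.)

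**5. Effect on the missing-at-random assumption.** If removal depended only on depression scores already recorded, the mixed model would address it. The bullet instead turns on the investigator's opinion about an adverse event or condition, which the recorded scores need not reflect. If later depression would have been worse in such participants than their recorded scores predict, the assumption fails. The text makes this possible but does not show that it will happen.

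**6. Scale, on assumed inputs only.** For a mean over completers alone, with k of n participants removed and a true mean change D standard deviations worse in those removed:

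completer mean − all-participant mean = (k / n) × D

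The Outcomes section expects more than 80% completion, and Recruitment expects 30 to 60 participants. 48/60 = 80.0% is not above 80%, so at least 49 of 60 must complete, leaving at most 11 non-completers. Likewise 24/30 = 80.0%, so at least 25 of 30 must complete, leaving at most 5. Taking D = 0.5 to 1.0 as an assumption:

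- k = 3, n = 60: 0.05 × D = 0.025 to 0.05 SD
- k = 3, n = 30: 0.10 × D = 0.05 to 0.10 SD
- k = 11, n = 60 (every permitted non-completer is such a removal): 0.183 × D = 0.09 to 0.18 SD
- k = 5, n = 30 (likewise): 0.167 × D = 0.08 to 0.17 SD

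A completers-only mean is not the planned analysis. The mixed model keeps pre-removal scores, and its bias depends on how far missing at random fails. These figures show scale only and are not an estimate.

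**The case against.** The best defence is that the beverage wording is leftover template text and the rest is ordinary. The rule is permissive, unnecessary withdrawal is discouraged, reasons are documented, and item 2 (Institutional Review Board) sends serious and unexpected adverse events to the IRB. Undue risk is a normal safety ground. The bullet on medical or compliance reasons already gives the investigator wide discretion, so deleting the effect-evaluation phrase alone would change little. All of this stands. The last point is why the remedy must rest on continued data collection, whichever bullet is used.

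A reader might go further and infer several things that the document does not support:

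- **That people who react badly are dropped from the results.** No passage excludes data already collected. Pre-removal scores can enter the mixed model, and analysis-set rules may sit in a plan not shown. Only post-removal data are at risk.
- **That staff remove participants after seeing their bi-weekly scores.** PHQ-9 is collected online, and no passage says that the investigator reviews it before deciding on removal. Removal driven by recorded scores would in any case be the situation the mixed model handles.
- **That the rule flatters the completion outcome.** A removed participant is a non-completer, so each removal lowers completion, by 1/60 = 1.7 or 1/30 = 3.3 percentage points.

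The defence does not answer the gap in follow-up. Documenting a reason does not replace the later scores and side-effect reports.

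**Conclusion.** The point holds in a limited form. The bullet names the wrong intervention. Read as the diet, it permits the end of study participation on a ground that concerns the effect evaluation rather than the participant's safety. Nothing commits the study to complete the observations of those whom the investigator removes. Post-removal PHQ-9, HRSD and side-effect data may be lost for outcome-related reasons, which strains the missing-at-random assumption and thins the safety information.

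How much data is at risk can be read from Table 1: for removal before week 6, both post-baseline HRSD assessments and both side-effect surveys. The size of any bias cannot be derived from the document, because it gives neither a number of such removals nor how those participants would have fared. The range above rests on assumed values of both and on a completers-only mean.

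The wrong noun alone would be a clerical correction. The missing follow-up commitment is what makes an amendment worthwhile.

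**What to change.** Amend item 5 of Conduct of the Study in four respects:

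1. Reconcile the third bullet with the intervention the trial actually tests.
2. State that possible interference with the effect evaluation is not a ground for ending data collection.
3. Distinguish stopping the diet from leaving the study.
4. Extend the complete-observations sentence to investigator-initiated removals. The online PHQ-9 and WHO-5, the scheduled HRSD and the side-effect survey would continue to week 12 unless the participant withdraws consent. Report the number of adverse-event-related removals, with reasons, among the safety results.

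When a participant should stop the diet is left to the sponsor, and no clinical rule is proposed here.

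The cost is a short amendment with IRB review. A few participants would continue questionnaires and already scheduled assessments after stopping the diet. PHQ-9 and WHO-5 are already online and HRSD may be done virtually, so the added burden is small.
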